6.9.2. Prohibited Medications and Non-Drug Therapies

Use of the medications listed in [Table 4](#) is not permitted during the study.

Table 4 Concomitant Medications

Medication	No use during the study and/or within the following time interval before Visit 1
Inhaled short-acting anticholinergics	6 hours
Inhaled short-acting anticholinergics+ Short-acting beta agonist combination	6 hours
Inhaled long-acting anticholinergics other than study treatment	2 days. Temporary use during the study is also prohibited.
Immunosuppressive medications including immunomodulators	12 weeks
Inhaled long-acting beta ₂ -agonists (e.g., salmeterol, formoterol) or combination products containing inhaled long-acting beta ₂ -agonists (e.g., Seretide, Symbicort)	These must be withheld at least 24h prior to Visit 1; other than the study treatment, they will not be permitted during the study (including for temporary use). 10 days prior to Visit 1 for Indacaterol and Olodaterol component. Temporary use during the study is also prohibited.
Inhaled very long-acting beta ₂ -agonists, (Indacaterol, Olodaterol) Oral long-acting beta ₂ -agonists (e.g., bambuterol)	
Inhaled short-acting beta ₂ -agonist (rescue albuterol/salbutamol will be provided and is permitted during the study)	6 hours (including all study visits)
Theophyllines, slow-release bronchodilators, ketotifen, nedocromil sodium, sodium cromoglycate, roflumilast	48 hours. Temporary use will be permitted during the study to treat moderate asthma exacerbations
Anti-leukotrienes	48 hours. Temporary use will be permitted during the study to treat moderate asthma exacerbations
Medical marijuana	6 months. Medical marijuana administered via the inhaled route is strictly prohibited. Other routes of administration of medical marijuana are also prohibited UNLESS written permission is obtained from the Medical Monitor prior to Visit 1.
Any other investigational drug	30 days or within 5 drug half-lives of the investigational drug (whichever is longer)

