7. STUDY ASSESSMENTS AND PROCEDURES

Protocol waivers or exemptions are not allowed with the exception of immediate safety concerns. Therefore, adherence to the study design requirements, including those specified in the Time and Events Table, are essential and required for study conduct.

This section lists the procedures and parameters of each planned study assessment. The exact timing of each assessment is listed in the Time and Events Table Section [7.1](#).

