7.3.4. Pulmonary Function Tests

Spirometry will be performed at the study site to assess FEV₁ and FVC. At least 3 acceptable spirometry manoeuvres (from a maximum of 8 attempts) should be achieved

on each occasion that spirometry assessments are performed, in accordance with the ATS/ERS standards [Miller 2005]. The highest of 3 technically acceptable measurements will be recorded at each visit:

- **Pre-dose Spirometry:** At Visits 3 through 8/EOS (and the Early Withdrawal Visit, if applicable), subjects should withhold short-acting beta-2-agonists (SABAs) for ≥ 6 hours prior to the clinic visit, if possible. Spirometry assessments must be performed:
 - Between 6am and 11am on the day of the visit.
 - At the same time of day (± 1 hour) as the assessment performed at Visit 3 (the baseline assessment).
 - At least 24 hours after the subject's last morning dose of study treatment on the day prior to the visit.
 - Before the subject's morning dose of study treatment on the day of the visit.
- **Post-dose Spirometry:** At Visits 3, 6 and 8/EOS (and the Early Withdrawal Visit, if applicable), spirometry assessments must be performed 3 hours after the subject's morning dose of study treatment; the assessment performed at Visits 6 and 8/EOS should be performed at the same time of day (± 1 hour) as the assessment performed at Visit 3 (the baseline assessment). At each visit, subjects should withhold short-acting beta-2-agonists (SABAs) between receiving their morning dose of study treatment and completing the spirometry assessments, if possible.

Spirometry equipment will be provided to all sites by a third-party vendor; the same third-party vendor will also centrally analyse the spirometry data from this study. Details on performing the spirometry assessments, including information on the equipment provided and its use as well as specific instructions on performing the spirometry manoeuvres, are documented in the SRM and the third-party vendor manual.

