### **6.3. Concomitant Medications**

Summaries will be provided for the asthma medications at

- Study entry
- During the screening/run-in period
- During the stabilisation period
- On-treatment period
- Post-treatment period
- Post-study period
- Asthma medication tables will report by respiratory medication class (RMC) and ingredient

Non-asthma medications will be summarized for the:

- On-treatment period
- Post-treatment period
- Post-study period

Non-Asthma medication tables will report by Anatomical Therapeutic Chemical (ATC) level 1 and ingredient. Multi-ingredient medications will be presented according to their combination ATC classification rather than the classification of the ingredients.

Listings will be provided for the asthma and non-asthma concomitant medications.

At study entry, asthma maintenance therapy containing inhaled corticosteroid (ICS), long-acting beta-2-agonist (LABA) long-acting muscarinic antagonist (LAMA), oral corticosteroid (OCS), leukotriene receptor antagonist (LTRA), xanthines (oral prescription only) or biologic will also be summarized and combinations presented. An “other” category will also be presented including nedocromil or cromolyn sodium. Combination therapies may be in a single inhaler or separate inhalers. A similar table will be produced to display maintenance therapy following IP discontinuation.

In addition, the asthma maintenance therapy at study entry will be presented by pooled FF treatment groups

The concomitant medications used for the treatment of moderate and severe asthma exacerbations during the study will also be summarized. These include, but not limited to, the protocol permitted concomitant medications of inhaled corticosteroids (including but not limited to the use of study provided FP), the systemic corticosteroids (tablets, suspension or injection), an investigator-advised change in SABA use (i.e., routinely scheduled versus as needed use), leukotriene receptor antagonists (LTRAs) and leukotriene modifiers, and oral xanthines.

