**7.1.6. Statistical Methodology Specification**

Primary Statistical Analyses
Endpoint

 
• Mean change from baseline in trough FEV1 at Week 24
 

Primary Model Specification

 
• Mixed Models Repeated Measures (MMRM) model.
 
• The analysis is based on ‘de facto’ type estimand, based on the ITT population.
 
• Clinic trough FEV1 (both on- and post-treatment) data collected prior to and at Week 24 will be included in the analysis.
 
• No imputation is made on missing data.
 

Primary Statistical Analyses

 
• While missing data are not explicitly imputed in the MMRM analyses, there is an underlying assumption that the data are missing at random. All available data will be utilized via modeling of the within-participant correlation structure, the derived treatment differences will be adjusted to take into account the missing data.
 
• Terms in the model: 
 
○ Dependent Variable: change from baseline in trough FEV1 at each visit
 
○ Covariates: 
 
▪ Categorical: treatment group, sex, region, visit, pre-study ICS dosage at screening,
 
▪ Continuous: age, baseline value for clinic FEV1
 
 
 
○ Interaction: baseline*Visit, treatment*Visit
 
○ Repeated: Visit
 
 
 
• The model will be fit with an unstructured variance-covariance matrix.
 
• The LS mean trough FEV1 and LS mean change from baseline in trough FEV1 will be estimated using the observed marginal distributions of the study population covariates by inclusion of the OM (observed margins) dataset in SAS.
 

Model Checking & Diagnostics

 
• Refer to Appendix 8: Model Checking and Diagnostics for Statistical Analyses.
 

Model Results Presentation

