**11.6.3. Efficacy**

Spirometry
Trough FEV1 and FVC

 
The trough value for FEV1 at Weeks 4, 12, 24, 36 and 52 visits is the value of the pre-dose (prior to taking the morning dose of study treatment) assessment.
 

Post study treatment FEV1

 
The post study treatment value for FEV1 at Week 24 and at the End of Study visit is the assessment value approximately 3 hours after administering the study medication.
 

Trough FEV1 over time

To evaluate the effect of UMEC over the first 24 weeks of the treatment period, the (weighted) mean trough FEV1 over the first 24 weeks of the treatment period will be calculated as the FEV1 area under the curve (AUC0-24w) normalized for time. Specifically, FEV1 weighted mean AUC0-24w will be calculated based on all non-missing data as area under the curve from day 1 to week 24 using the linear trapezoidal rule divided by the observation time (24 weeks) to report in liter (L) units. If one or more observations are missing between two non-missing observations, the value(s) will be linearly interpolated between the two non-missing values.
 
The weighted mean AUC0-24w will be calculated over the nominal assessment time per protocol as follows:
 $WM\ FEV_1\ AUC_{0-24w} = \frac{\frac{1}{2} \sum_{i=0}^3 (FEV_1(t_i) + FEV_1(t_{i+1})) * (t_{i+1} - t_i)}{24w}$ 
Where, t0 = 0 (week), t1= 4 (week), t2=12 (week), and t3=24 (week); FEV1 (t0) = baseline trough FEV1, and for i>0, FEV1 (ti) = trough FEV1 reading at planned week ti.
 
If baseline, week 24 or any two timepoints are missing the AUC will not be calculated.

Asthma Exacerbations		
General		

 
Exacerbations will be presented based on onset date relative to the period being summarized. i.e. if the onset date occurs within the study period then it will be reported within that study period)
 
 
The following data will be included in the exacerbation analyses and summaries
		
Analysis	Time point	Data to be included (i.e. from participants first dose up to date/study day specified)

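### The protocol's bar on non-study LABA and LAMA is never lifted in writing for subjects who stop double-blind treatment but stay in follow-up, which conflicts with SAP 11.7.1

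*Protocol*

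**What the plan says.** Protocol 6.9.2 opens by saying that the medications in Table 4 may not be used during the study. For LABA, including combinations with ICS, the table adds "other than the study treatment, they will not be permitted during the study (including for temporary use". The LAMA row gives a washout before Visit 1 and likewise rules out temporary use. Theophyllines and anti-leukotrienes are treated differently: they may be used temporarily for moderate exacerbations. ICS alone is not in the table.

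Protocol 6.9 lets subjects who have completed the Early Withdrawal Visit take anything their physician prescribes. Note 4 in section 7.1 says that this visit applies when double-blind treatment is stopped and the subject also leaves the study. Sections 4.1 and 5.6.1 ask subjects who stop treatment to remain and be followed as per protocol. Neither says what asthma therapy they may then take. On departures, section 7 states: "Protocol waivers or exemptions are not allowed with the exception of immediate safety concerns".

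SAP 11.7.1 has subjects who stop double-blind treatment followed to the end of the study after going back to suitable asthma therapy at the investigator's discretion. SAP 6.3 describes a study-entry table: "At study entry, asthma maintenance therapy containing inhaled corticosteroid (ICS), long-acting beta-2-agonist (LABA) long-acting muscarinic antagonist (LAMA" and further classes. It then adds: "A similar table will be produced to display maintenance therapy following IP discontinuation". That output is Table 1.45. SAP 7.1.4 keeps data after discontinuation whatever treatment switches occur.

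**The concern.** Every subject enters with a clinical need for daily ICS/LABA (protocol 4.4 and inclusion criterion 5) and with inadequately controlled asthma. When such a subject stops double-blind treatment, the LABA in the study inhaler stops too. A site reading Table 4 literally then has two choices: leave the subject without a maintenance LABA, or prescribe standard care and record a protocol deviation. Some of these subjects do not choose to stop, for example after a positive pregnancy test or on meeting a QTc criterion (5.6.1).

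Two things are at stake: the safety of subjects selected because they need this class of drug, and their willingness to stay in the study. The second matters to the analysis. The primary and key secondary analyses use a treatment-policy strategy, which depends on data collected after treatment stops.

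**Working it through.** No arithmetic applies. The check is whether any sentence in the protocol releases a retained discontinuer from Table 4, and whether the SAP agrees.

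1. **Does the bar reach the off-treatment period?** Table 4 is worded in terms of the study, not of treatment. Section 6.9, where it sets out which asthma medications to record, uses the same phrase and states that it includes the post-treatment period. On the protocol's own usage, the bar extends past the last dose of study drug.

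2. **Does the release in 6.9 cover these subjects?** It requires a completed Early Withdrawal Visit. Note 4 gives that visit only to subjects who stop treatment and leave the study. Someone who stops treatment and stays has no such visit, so the release does not apply. An express release for those who leave, with none for those who stay, strengthens the literal reading.

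3. **Does any other provision restore a maintenance LABA?**
   - 6.9.1.1 lists temporary additions for moderate exacerbations. The list is open-ended, but Table 4 specifically refuses temporary LABA and LAMA use.
   - 7.3.6.1 lets additional therapy continue after a second moderate exacerbation. It concerns exacerbation treatment and does not lift the LABA bar.
   - 6.8 deals with care after the study is complete.
   - 5.6.1 is silent on subsequent asthma therapy and refers to the SRM.

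   None of them does.

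4. **What does the SAP assume?** SAP 11.7.1 has these subjects back on suitable asthma therapy while still followed. It does not name LABA, but the entry criteria make ICS/LABA the established maintenance therapy of this population. The protocol withholds what 11.7.1 takes for granted.

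5. **Is the difference acknowledged?** SAP 2.1 lists changes from the protocol-defined analysis. It does not mention this one.

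Result: the protocol text contains no release for this group, and SAP 11.7.1 presupposes one.

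**The case against.** The best reply is that the literal reading was never intended. Table 4 is headed as a list of concomitant medications, its LABA row makes an exception for study treatment, and 6.9.1.1 describes permitted drugs as additions to study treatment. All of this suggests a rule for subjects who are still taking double-blind drug. Section 6.9 has post-treatment asthma medication recorded, so such use was expected. Sections 5.6.1 and 6.9 both point to the SRM, which may settle the matter. LABA use triggers no mandatory withdrawal, section 7 exempts immediate safety concerns, and SAP 11.1 plans no per-protocol analysis, so a deviation label would not remove a subject from the efficacy analyses.

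Most of this stands as evidence of intent and as a limit on the harm. It does not supply the missing sentence. Routine maintenance therapy should not have to rest on a safety exception or on a manual outside the protocol.

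Two stronger readings are tempting and are not supported.

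- **That SAP 7.1.4 and 6.3/Table 1.45 also contradict Table 4.** They do not. A treatment-policy strategy and a descriptive table can handle any medication use, permitted or not. They presuppose such use without conflicting with the bar.
- **That the primary endpoint is compromised.** Spirometry timing in protocol 7.3.4 is tied to the "last morning dose of study treatment on the day prior to the visit", and the primary model takes trough FEV1 "both on- and post-treatment) data collected prior to and at Week 24 will be included in the analysis". A reader might infer that a resumed LABA distorts trough FEV1. Under treatment policy, however, values after a switch are meant to count as they are. Standardising the timing of a replacement bronchodilator is a debatable preference, and no bias can be derived from the documents.

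**Conclusion.** The point holds as a conflict between protocol 6.9.2/6.9 and SAP 11.7.1. As written, the protocol keeps non-study LABA (including ICS/LABA) and LAMA off limits for subjects who stop double-blind treatment and remain in follow-up, while the SAP has them back on suitable therapy. LABA is the main issue, because entry required ICS/LABA and not a LAMA.

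Its size cannot be stated. The documents give neither the number of such subjects nor any effect on an estimate, and none is claimed. A reader might multiply out the visit schedule to get weeks spent under the bar, but that would only restate the literal reading and would not measure harm. Nor do the documents show that any subject went without a LABA.

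The conclusion rests on two assumptions: that *during the study* in Table 4 carries the meaning it has in 6.9, and that the protocol governs wherever the SRM might differ. If the SRM already contains the release, what remains is a misalignment between the two documents.

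**What to change.** In protocol 6.9, and by a note to Table 4, state that the prohibition of non-study LABA (including ICS/LABA) and LAMA ends when double-blind treatment is permanently discontinued, and that from then on asthma maintenance therapy is at the investigator's discretion and is recorded in the eCRF. Leave the pre-Visit 1 washout intervals in Table 4 as they are. If the SRM already says this, bring the protocol into line with it.

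The cost is one short protocol amendment. SAP 11.7.1 already assumes the release and needs no change. There are no added patients, visits or procedures, and no effect on alpha, power or sample size.

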7. STUDY ASSESSMENTS AND PROCEDURES

Protocol waivers or exemptions are not allowed with the exception of immediate safety concerns. Therefore, adherence to the study design requirements, including those specified in the Time and Events Table, are essential and required for study conduct.

This section lists the procedures and parameters of each planned study assessment. The exact timing of each assessment is listed in the Time and Events Table Section [7.1](#).

7.1. Time and Events Table

Protocol Activity	Pre-Screen ¹	Screen Run-in	Enrolment Stabilization	Treatment Period						Follow-up	
				Fixed Treatment Period				Variable Treatment Period		Early Withdrawal (EW) ⁴	Safety Follow-up Contact
Visit	0	1 ¹	2 ²	3 ³ Randomization	4	5	6	7	8 End of Study (EOS)		
Study Day	-49 to -36	-35	-14	1	29	85	169	253	365		
Week	-6 to -7	-5	-2	0	4	12	24	36	52		1 week after Visit 8/EOS or EW Visit
Window					-5/+2d	-5/+2d	-5/+2d	-5/+2d	-5/+2d		-1/+4d
Written Informed Consent ⁵	x										
Genetic Informed Consent ⁶	x										
Demography	x										
Medical history		x									
Asthma History ⁷		x									
Exacerbation History		x									
Concomitant Medication Assessment	x	x	x	x	x	x	x	x	x	x	x
Inclusion/Exclusion criteria		x	x								
Smoking History and status		x									
Randomization ⁸				x							
Register visit in IRT (RAMOS NG) ⁹	x	x	x	x	x	x	x	x	x	x	x
Efficacy Assessments											
Global Assessment of Severity ¹⁰				x	x	x	x	x	x	x	

Protocol Activity	Pre-Screen ¹	Screen Run-in	Enrolment Stabilization	Treatment Period						Follow-up	
				Fixed Treatment Period				Variable Treatment Period		Early Withdrawal (EW) ⁴	Safety Follow-up Contact
Visit	0	1 ¹	2 ²	3 ³ Randomization	4	5	6	7	8 End of Study (EOS)		
Study Day	-49 to -36	-35	-14	1	29	85	169	253	365		
Week	-6 to -7	-5	-2	0	4	12	24	36	52		1 week after Visit 8/EOS or EW Visit
Window					-5/+2d	-5/+2d	-5/+2d	-5/+2d	-5/+2d		-1/+4d
Global Assessment of Response to Treatment ¹⁰					x	x	x	x	x	x	
ACQ ¹⁰		x	x	x	x	x	x	x	x	x	
SGRQ ¹⁰				x		x	x	x	x	x	
AQLQ ¹⁰				x	x	x	x	x	x	x	
Healthcare Resource Utilization ¹⁰				x	x	x	x	x	x	x	
E-RS + asthma symptoms + PEF + home FEV ₁ ^{10, 11}											x
eDiary/device training and registration		x									
Dispense eDiary		x									
Collect eDiary									x	x	
eDiary review			x	x	x	x	x	x	x	x	
Dispense paper Medical Problems/Medications Taken worksheet	x	x	x	x	x	x	x	x	x	x	

Protocol Activity	Pre-Screen ¹	Screen Run-in	Enrolment Stabilization	Treatment Period						Follow-up	
				Fixed Treatment Period			Variable Treatment Period			Early Withdrawal (EW) ⁴	Safety Follow-up Contact
Visit	0	1 ¹	2 ²	3 ³ Randomization	4	5	6	7	8 End of Study (EOS)		
Study Day	-49 to -36	-35	-14	1	29	85	169	253	365		
Week	-6 to -7	-5	-2	0	4	12	24	36	52		1 week after Visit 8/EOS or EW Visit
Window					-5/+2d	-5/+2d	-5/+2d	-5/+2d	-5/+2d		-1/+4d
Review paper Medical Problems/Medications Taken worksheet		x	x	x	x	x	x	x	x	x	x
Pre-dose spirometry (clinic)		x ¹²	x ¹²	x ¹³	x ¹²	x ¹²	x ¹³	x ¹²	x ¹³	x ^{13, 14}	
Post-dose spirometry (clinic)				x ¹³			x ¹³		x ¹³	x ^{13, 14}	
Reversibility test		x ¹⁵	x ¹⁶								
Exacerbation assessment			x	x	x	x	x	x	x	x	x
Health Outcomes											
WPAI-SHP ¹⁰				x		x	x		x	x	
Safety Assessments											
Physical Examination		x					x		x	x	
Vital Signs		x ¹⁷	x	x	x	x	x	x	x	x	
ECG ¹⁸		x			x		x		x	x	
Adverse Events		x	x	x	x	x	x	x	x	x	x

Protocol Activity	Pre-Screen ¹	Screen Run-in	Enrolment Stabilization	Treatment Period						Follow-up	
				Fixed Treatment Period			Variable Treatment Period				
Visit	0	1 ¹	2 ²	3 ³ Randomization	4	5	6	7	8 End of Study (EOS)	Early Withdrawal (EW) ⁴	Safety Follow-up Contact
Study Day	-49 to -36	-35	-14	1	29	85	169	253	365		
Week	-6 to -7	-5	-2	0	4	12	24	36	52		1 week after Visit 8/EOS or EW Visit
Window					-5/+2d	-5/+2d	-5/+2d	-5/+2d	-5/+2d		-1/+4d
Serious Adverse Events	x	x	x	x	x	x	x	x	x	x	x
FeNO ¹⁹				x							
Laboratory Assessments											
Hematology and clinical chemistry		x				x	x		x	x	
Total Serum IgE		x									
Urinalysis		x				x	x		x	x	
Pharmacogenetic sample ²⁰				x							
Serum pregnancy test		X ²¹					x ²¹		x ²¹	x ²¹	
Urine pregnancy test ²¹			x	x	x	x		x			
PK samples						x ²²	x ²³		x ^{23, 24}	x ²³	
Study Treatment											
Dispense ICS/LABA run-in medication		x ²⁵									

Protocol Activity	Pre-Screen ¹	Screen Run-in	Enrolment Stabilization	Treatment Period						Follow-up	
				Fixed Treatment Period			Variable Treatment Period			Early Withdrawal (EW) ⁴	Safety Follow-up Contact
Visit	0	1 ¹	2 ²	3 ³ Randomization	4	5	6	7	8 End of Study (EOS)		
Study Day	-49 to -36	-35	-14	1	29	85	169	253	365		
Week	-6 to -7	-5	-2	0	4	12	24	36	52		1 week after Visit 8/EOS or EW Visit
Window					-5/+2d	-5/+2d	-5/+2d	-5/+2d	-5/+2d		-1/+4d
Assess run-in medication compliance			x								
Collect ICS/LABA run-in medication			x								
Dispense ICS/LABA stabilization medication			x								
Assess stabilization medication compliance				x							
Collect ICS/LABA stabilization medication				x							
Administer double-blind study treatment ²⁶				x	x	x	x	x	x	x ²⁷	
Dispense double-blind study treatment (Scheduled)				x	x	x	x	x			
Dispense double-blind study treatment (Unscheduled)				x ²⁸							
Assess double-blind study treatment compliance					x	x	x	x	x	x	

Protocol Activity	Pre-Screen ¹	Screen Run-in	Enrolment Stabilization	Treatment Period						Follow-up	
				Fixed Treatment Period			Variable Treatment Period			Early Withdrawal (EW) ⁴	Safety Follow-up Contact
Visit	0	1 ¹	2 ²	3 ³ Randomization	4	5	6	7	8 End of Study (EOS)		
Study Day	-49 to -36	-35	-14	1	29	85	169	253	365		
Week	-6 to -7	-5	-2	0	4	12	24	36	52		1 week after Visit 8/EOS or EW Visit
Window					-5/+2d	-5/+2d	-5/+2d	-5/+2d	-5/+2d		-1/+4d
Collect double-blind study treatment (Scheduled)					x	x	x	x	x	x	
Collect double-blind study treatment (Unscheduled)				x ²⁹							
Dispense albuterol/salbutamol, as required		x	x	x	x	x	x	x			
Collect albuterol/salbutamol, as required			x	x	x	x	x	x	x	x	
Dispense FP, as required ³⁰		x	x	x	x	x	x	x			
Collect FP, as required			x	x	x	x	x	x	x	x	

Notes:

1. Visit 1 should be completed ≥ 1 day but ≤ 14 days after Visit 0; however, if it is local and routine medical practice to request that a subject withhold their ICS/LABA medication for at least 24 hours prior to a clinic visit then, provided that the subject has complied with the request, Visit 0 and Visit 1 can occur on the same day.
2. Visit 2 may be conducted up to 3 days before the scheduled date of Visit 2. The duration of the run-in period (i.e. the time period between Visits 1 and 2) must be ≥ 18 days but ≤ 26 days.
3. Visit 3 must always be conducted ≥ 14 days but ≤ 17 days after Visit 2.
4. EW Visit should be conducted if double-blind study treatment is discontinued AND the subject discontinues from participating in the study.
5. The ICF must be signed before any study procedures, including protocol-specified medication cessation.
6. Genetics research consent may be obtained at the same time as the study IC and must be obtained prior to obtaining a genetic blood sample.

7. The assessment of asthma history will include: the age of the subject when they were first provided with an inhaler for asthma; completion of an asthma medical history questionnaire (a copy of this questionnaire and instructions for its use can be found in the SRM).
8. Subjects must not be randomised prior to confirming their eligibility to participate in the study.
9. The IRT will be used for randomization, emergency unblinding and study treatment supply management (Please refer to the RAMOS NG IRT manual and SRM for more information).
10. Assessment(s) to be completed prior to the administration of study treatment.
11. To be completed using the provided combined spirometer/eDiary device. Assessments should be completed in the morning upon waking and in the evening immediately prior to going to bed.
12. Spirometry to be performed between 6am and 11am after withholding rescue medication for at least 6 hours and prior to taking the morning dose of study treatment. Pre-dose spirometry assessments should be performed at the same time of day at each applicable visit.
13. Pre-dose spirometry to be performed between 6am and 11am, prior to taking the morning dose of study treatment. Post-dose spirometry is to be performed 3 hours (± 15 minutes) after taking the morning dose of study treatment. Rescue medication should be withheld for at least 6 hours prior to the pre-dose spirometry assessments until after completion of the 3-hour post-dose spirometry assessments. Pre- and post-dose spirometry assessments should be performed at the same time of day at each applicable visit.
14. In the event that double-blind study treatment is not administered at this visit, spirometry assessments should be performed at the same time of day as the pre- and post-dose spirometry assessments at the preceding on-treatment clinic visits.
15. Following completion of the pre-dose spirometry assessments, the reversibility test will be conducted between 20 and 60 minutes following 4 inhalations of albuterol/salbutamol aerosol. If airway reversibility is not demonstrated at Visit 1 then the assessment may be repeated within 7 days of Visit 1 (see Section 7.3.4.1.1 for details of the criteria to be met before a repeat of the reversibility assessment is permitted). If airway reversibility is successfully demonstrated at the second attempt and all other eligibility criteria assessed at Visit 1 are met then the subject may commence the 3-week run-in period (starting on the date that airway reversibility was successfully demonstrated at the second attempt).
16. Following completion of the pre-dose spirometry assessments, the reversibility test will be conducted between 60 and 90 minutes following 4 inhalations of ipratropium aerosol (see Section 7.3.4.1).
17. The vital signs assessment will include the measurement of height and weight at this visit only.
18. At the Screening Visit (Visit 1), the ECG is to be obtained after the vital signs assessment but prior to performing the pre-bronchodilator spirometry assessment (see Section 7.5.6). At all post-randomization visits the ECG is to be obtained 15 minutes to 45 minutes after the administration of study treatment.
19. Exhaled Nitric Oxide is widely accepted as a non-invasive marker for airway inflammation and will be assessed to characterise the study subject population. Details on performing the FeNO assessment, including information on the equipment provided and its use, are documented in the SRM and the third-party vendor manual.
20. Pharmacogenetic sample may be drawn any time from Visit 3 onwards.
21. Assessments only to be conducted in females of reproductive potential.
22. Pharmacokinetic (PK) subset: In a subset of approximately 20% of all randomized subjects, PK samples will be obtained at pre-dose on the visit day, and 1 sample in each of the following three time windows: 5min-30min, 45min-90min, and 2-3h post dose on the visit day. NOTE: the date and time of study treatment administration on the day prior to the visit must be recorded in the eCRF.
23. PK sample to be obtained at pre-dose on the visit day (This PK sample is to be obtained from ALL study subjects). NOTE: the date and time of study treatment administration on the day prior to the visit must be recorded in the eCRF.
24. PK sample to be obtained at this visit ONLY in the event that Visit 8/EOS assessments are conducted at Week 24.
25. In the event that the reversibility assessment needs to be repeated within 7 days of Visit 1 (see Section 7.3.4.1.1) then the medication for the 3-week run-in period must not be dispensed until airway reversibility is successfully demonstrated at the second attempt and all other eligibility criteria assessed at Visit 1 are confirmed as met.
26. Study treatment should be administered at the same time of day at each applicable clinic visit.

27. The administration of study treatment at this visit is optional. If study treatment is not administered at this visit then those assessments which are scheduled based on the time of study treatment administration should be performed at approximately the same time of day as performed at the preceding post-randomization visits.
28. Between scheduled visits, unscheduled visits to the study clinic to re-supply the subject with double-blind study treatment is permitted after Visit 3 but before Visit 8/EOS. The IRT will be used for study treatment supply management (Please refer to the RAMOS NG IRT manual and SRM for more information).
29. In the event that the subject attends the study clinic for the unscheduled dispensing of double-blind study treatment, previously dispensed study treatment should be collected for drug accountability purposes.
30. FP may be used temporarily to treat the symptoms of a moderate asthma exacerbation, at the Investigator's discretion. However, please note that a subject's use of the provided FP prior to randomization at Visit 3 would meet the enrolment or randomization concomitant medication exclusion criteria (see Section 5.3.2 and Section 5.4.2)

